### 3. PRIMARY HYPOTHESIS

#### 3.1. Primary Hypothesis #1: Impact of Early GDM Screening on the Primary Outcome (a Composite of Key Perinatal Outcomes)

*H0: There will be no difference in the rate of the primary outcome (quantified by the composite outcome of key perinatal outcomes) in EGGO participants randomized to the Early screening group compared to participants randomized to the Routine screening Group.*

**3.1.1. Primary Outcome:** The primary outcome is a composite of the following items: macrosomia, primary cesarean, pregnancy induced hypertension (gestational hypertension or preeclampsia), shoulder dystocia, neonatal hyperbilirubinemia, and neonatal hypoglycemia. The occurrence of 1 or more of these items will be considered an occurrence of the primary study outcome. Individual definitions of these outcomes are listed below.

- a. Macrosomia: Will be defined by measurement of infant birth weight. Macrosomia is a birth weight >4000 g.
- b. Primary cesarean: A primary cesarean delivery for any indication will be considered as having the outcome of interest.
- c. Gestational hypertension: Defined by systolic blood pressure  $\geq 140$  or diastolic blood pressure  $\geq 90$  without proteinuria (urine protein/creatinine ratio  $< 0.19$  or mg).
- d. Preeclampsia: Defined by systolic blood pressure  $\geq 140$  or diastolic blood pressure  $\geq 90$  with proteinuria (urine protein/creatinine ratio  $\geq 0.30$ ). Preeclampsia diagnosis will also be refined by mild or severe. Severe preeclampsia will be defined as systolic blood pressure  $\geq 160$ , diastolic blood pressure  $\geq 110$ , platelets  $< 100$ , AST  $> 80$  serum creatinine  $> 1.2$ .
- e. Shoulder dystocia: As documented by delivering physician; defined as requiring more than routine downward traction to achieve delivery of anterior shoulder. The length of the shoulder dystocia and maneuvers required to relieve the shoulder dystocia will be documented.
- f. Neonatal hyperbilirubinemia: Neonatal bilirubin levels will be recorded. Hyperbilirubinemia will be defined  $> 95$ th percentile gestational age and hour of life. The treatment of hyperbilirubinemia (i.e. phototherapy) will also be recorded.
- g. Neonatal hypoglycemia. Blood sugar levels will be abstracted from neonatal charts. Neonatal hypoglycemia will be defined as blood sugar  $< 35$ mg/dL.

**3.1.2. Analysis Plan:** This hypothesis effect of Early versus Routine GDM screening in obese pregnant women. The  $\chi^2$  test of association will be used to evaluate whether the rate of the primary outcome differs between the treatment groups. The primary analysis will be an intention-to-treat analysis of all individuals randomized to the two treatment groups, regardless of whether evaluation plans were followed. Risk ratios (RR) and 95% confidence intervals (CIs) will be computed and presented.

Standard comparison of the covariate characteristics at baseline between study groups will be undertaken (Section 2) to assess the randomization balance on measured covariates. Tests of significance will be two-sided and evaluated at the 0.05 level of significance. Since the sample size for EGGO is large, it is unlikely that “important” covariates (such as race, BMI or age) will be imbalanced through the

randomization process. Further, randomization is stratified by BMI (BMI <40 and BMI ≥40) and site (UAB and Oschsner).

In the unlikely event that imbalance occurs, adjustment for covariates will be made by modeling the log-odds of the outcome using multivariable logistic regression including terms indicating group membership and each of the imbalanced covariates. In other words, the log-odds of the primary outcome for any individual will be modeled using the following form:

$$\ln\left(\frac{P(\text{outcome})}{1-P(\text{outcome})}\right) = \beta_0 + \beta_1 x_1 + \sum \beta_j z_j.$$

Above,  $x_1 = 1$  if the patient is in the Early group and equals 0 if the patient is in the Routine group. The set of  $z_j$ 's consists of all covariates in the model including site. Hence, under this model, the term  $\beta_1$  represents the difference in the log-odds between the two groups. To address the hypothesis of interest for primary hypothesis #1, we will perform a statistical test of  $H_0: \beta_1 = 0$  vs.  $H_1: \beta_1 \neq 0$ . Quantification of the treatment effect will be performed by exponentiation of the estimated coefficient,  $\exp(\beta_1)$ , to obtain an estimate of the odds ratio. The confidence interval will be determined similarly.

The stratification by BMI and by site allows for the investigation of differential effects across sites and across BMI thresholds. The presence of a homogeneous effect across center and across BMI thresholds will be examined using the Breslow-Day test.

**3.1.3. Sample Size for Primary Outcome:** Based on prior studies performed at UAB, the incidence of macrosomia, cesarean delivery, shoulder dystocia, and preeclampsia in obese women with gestational diabetes was 56%. Using a conservative estimate of these outcomes as 50%, to detect a 50% reduction in the incidence of adverse outcomes ( $\alpha=0.05$ ,  $\beta=0.80$ ), 58 gestational diabetics per group are necessary.

The diagnosis of GDM will occur after patients in this study have been screened for GDM. As a result, a large number of patients must be randomized to each diagnostic procedure in order to achieve 58 gestational diabetics in each group. Prior reports of the incidence of GDM are between 6-20% depending on ethnicity and the screening and diagnostic criteria used. Using an incidence of 10% GDM in obese women, 580 subjects per screening group are necessary. Approximately 3,100 women per year attend the UAB clinic for obstetric visits, and approximately 40% of these women are obese. Assuming a 50% acceptance of enrollment, we anticipate enrolling 620 women per year. Therefore, we feel that we can enroll 1,160 subjects in 3 years.

**3.2. Interim Monitoring:** One interim analysis, evaluating both efficacy and futility, will be conducted after 600 women have completed the study (300 in each group have delivered). Under the assumption that 10% of obese women have GDM, we expect to have approximately 30 gestational diabetics in each group. Using an O'Brien-Fleming alpha spending function and one interim analysis, we will use the following critical stopping values:

At the interim look:     If  $\chi^2 > 7.82$  (i.e.  $p < 0.005$ ) then reject  $H_0$  and consider stopping the trial;  
                                  Otherwise, continue.

At the final look:        If  $\chi^2 > 3.91$  (i.e.  $p < 0.048$ ) then reject  $H_0$ .

We do not propose a formal stopping rule for safety or futility, but note that the DSMB will be presented with safety data and information on study progress. In addition, we note that the overall sample size of 58 gestational diabetics per group will provide 80% power for the hypothesized effect size using a modified alpha level of 0.048 at the final analysis. Conditional power estimates may be provided to assist the DSMB in their evaluation of efficacy and futility.

The interim analysis will focus only on outcomes specified in Section 3 of this Statistical Analysis Plan. Secondary outcomes may be presented at that time in aggregate form (only safety events will be presented by study group). Formal statistical hypothesis testing for those secondary outcomes will be conducted at the conclusion of the trial.

At the time of the interim analysis, the Ochsner study site will have contributed a small number of patients to the study. These patients will be excluded from the interim analysis evaluation.

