- a. Women with gestational diabetes will be contacted prior to their appointment by either phone or letter to remind them to come to their post-partum visit prepared for the fasting, 2-hour, 75-g glucose tolerance test.
- b. Women diagnosed with gestational diabetes will undergo a 2-hour, 75-g glucose tolerance test at the time of their post-partum visit at OBCC or resident continuity clinic. They will receive \$10 for undergoing this testing.
- c. All women will be asked whether they or their infant have been re-admitted to the hospital since the time of discharge and the reason for admission. Permission will be obtained to request records for re-admission diagnoses.

7. Outcome Measures

The primary outcome will be a composite outcome of macrosomia (birth weight >4000g), primary cesarean, gestational hypertension or preeclampsia, shoulder dystocia, neonatal hyperbilirubinemia, and neonatal hypoglycemia. Each of these outcomes will also be evaluated individually as secondary outcomes. Additional secondary outcomes will include premature delivery (<37wks).

- a. Macrosomia: Will be defined by measurement of infant birth weight. Macrosomia is a birth weight >4000 g.
- b. Primary cesarean: A primary cesarean delivery for any indication will be considered as having the outcome of interest.
- c. Gestational hypertension: Defined by systolic blood pressure ≥ 140 or diastolic blood pressure ≥ 90 without proteinuria (urine protein/creatinine ratio < 0.19 or 24-hour urine protein < 300 mg).
- d. Preeclampsia: Defined by systolic blood pressure ≥ 140 or diastolic blood pressure ≥ 90 with proteinuria (urine protein/creatinine ratio ≥ 0.19 or 24-hour urine protein ≥ 300 mg). Preeclampsia diagnosis will also be refined by mild or severe. Severe preeclampsia will be defined as systolic blood pressure ≥ 160 , diastolic blood pressure ≥ 110 , proteinuria ≥ 5000 mg in 24 hours or 3+ urine dip, platelets < 150 , AST > 60 , oliguria (< 500 mL urine/ 24 hours), pulmonary edema, creatinine > 1.0 .
- e. Shoulder dystocia: As documented by delivering physician; defined as requiring more than routine downward traction to achieve delivery of anterior shoulder. The length of the shoulder dystocia and maneuvers required to relieve the shoulder dystocia will be documented.

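### The SAP's hypertension items do not meet: raised blood pressure with a protein/creatinine ratio of 0.19 to below 0.30 is preeclampsia in the protocol but neither SAP item, so it drops out of the primary composite

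*SAP*

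**What the plan says.** SAP 3.1.1 lists pregnancy-induced hypertension, meaning gestational hypertension or preeclampsia, as one component of the primary composite and refers to the lettered items for the definitions. Its counting rule is: "The occurrence of 1 or more of these items will be considered an occurrence of the primary study outcome".

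Items c and d use the same blood pressure limits (systolic at least 140 or diastolic at least 90) and differ in proteinuria:

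- SAP item c, gestational hypertension: "without proteinuria (urine protein/creatinine ratio $< 0.19$ or mg"
- SAP item d, preeclampsia: "with proteinuria (urine protein/creatinine ratio $\geq 0.30$ ). Preeclampsia diagnosis will also be refined by mild or severe"

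Item d then lists severity criteria: blood pressure of 160 systolic or 110 diastolic, and "platelets $< 100$ , AST $> 80$ serum creatinine $> 1.2". None of them is a urine protein value.

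Protocol section 7 (Outcome Measures) uses the same blood pressure limits and one ratio cut-point, with a 24-hour alternative:

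- Protocol 7c: "without proteinuria (urine protein/creatinine ratio < 0.19 or 24-hour urine protein < 300 mg"
- Protocol 7d: "with proteinuria (urine protein/creatinine ratio ≥ 0.19 or 24-hour urine protein ≥ 300 mg"

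The composite is tested by chi-square in everyone randomized (SAP 3.1.2: "The primary analysis will be an intention-to-treat analysis of all individuals randomized to the two treatment groups"). SAP 3.2 ties the interim look to Section 3 outcomes and sets the final limit: "\chi^2 > 3.91$ (i.e. $p < 0.048$ ) then reject $H_0". SAP section 4 also analyses each component separately.

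**The concern.** The ratio bounds of two adjacent SAP items leave an interval that belongs to neither. A deliberate change of the preeclampsia cut-point in the 2017 SAP could explain 0.30 in item d. It would not explain keeping 0.19 in item c.

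What is at stake is event status in the primary endpoint. One component is enough for a primary event, so a woman in the interval with no other component changes from event to non-event depending on which document is applied. Two programmers working from the two documents would build different primary datasets. The same gap reaches the interim look and the component analyses. If nothing is changed, these women must be classified by a rule chosen later, possibly with results in view.

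**Working it through.** **1. Apply both rules.** Take a woman who meets the blood pressure criterion and has only a ratio.

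| Ratio | Protocol 7c-d | SAP 3.1.1c-d |
|---|---|---|
| 0.10, 0.18 | gestational hypertension | gestational hypertension |
| 0.19, 0.20, 0.25, 0.29 | preeclampsia | neither |
| 0.30, 0.40 | preeclampsia | preeclampsia |

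The uncovered interval is 0.19 ≤ ratio < 0.30.

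**2. Does other SAP text close it?**

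- *The fragment at the end of item c.* It may be what is left of a 24-hour criterion, and the loss may come from reading the PDF. Restored as in protocol 7c, it would cover only women with a 24-hour value below 300 mg. A woman with only a ratio would still be unassigned. So would a woman with a ratio in the interval and a 24-hour value of 300 mg or more, because item d as read has no 24-hour criterion.
- *The severity list in item d.* It grades a preeclampsia diagnosis already made. Read as a stand-alone route, it would still miss women in the interval who are below 160/110 and have none of the listed laboratory values.

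**3. Scale.** The documents give no rate for women in the interval with no other component, so the share g is an assumption. Affected women = 1,160 × g.

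- g = 0.5%: 5.8
- g = 1%: 11.6 (580 × 0.01 = 5.8 per arm)
- g = 2%: 23.2
- g = 3%: 34.8

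At the interim look, 1% of 600 is 6, before the Ochsner exclusion.

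**4. The plan's own sample size reproduces.** With 50% vs 25%, two-sided alpha 0.05, 80% power and pooled variance:

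n = [1.960 × √(2 × 0.375 × 0.625) + 0.842 × √(0.25 + 0.1875)]² / 0.25² = 57.7, so 58 per group; 58/0.10 = 580 randomized per group.

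At the final alpha of 0.048:

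power = Φ[(0.25 × √58 − 1.977 × 0.685) / 0.661] = 79.7%.

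**5. Direction of any power change.** Lower the event rates in that calculation by g:

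| g | Equal points lost in both arms | Proportional loss (risk ratio held at 0.50) |
|---|---|---|
| 0.5% | 79.9% | 79.1% |
| 1% | 80.2% | 78.4% |
| 2% | 80.7% | 77.0% |
| 3% | 81.2% | 75.6% |

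The sign depends on an assumption the documents cannot settle, so no power loss is asserted. This calculation concerns the 58 gestational diabetics per group, not the all-randomized test.

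**6. The planned test near its limit.** With 580 per group and a and b events (routine, early), and no continuity correction:

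χ² = 1160 × (a − b)² / [(a + b)(1160 − a − b)].

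Assume 290 vs 256: 1160 × 34² / (546 × 614) = 4.00, above 3.91. Now remove 12 women (about 1%), split routine/early:

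- 6/6: 284 vs 250, χ² = 4.01
- 7/5: 283 vs 251, χ² = 3.55, no longer significant
- 5/7: 285 vs 249, χ² = 4.50

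It can go the other way. An assumed 290 vs 257 gives 3.77, and a 5/7 split makes it 285 vs 250, χ² = 4.25, which is significant.

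**7. How often the decision would change.** Simulation with 580 per group, limit 3.91, an assumed 50% routine rate, and each event removed with probability g/0.50 in both arms:

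| True rates | g = 0.5% | 1% | 3% |
|---|---|---|---|
| 50% vs 50% | 1.3% | 1.8% | 3.1% |
| 50% vs 47.5% | 2.4% | 3.4% | 5.8% |
| 50% vs 44.1% | 4.3% | 6.3% | 11.3% |

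The second row confines the SAP's 25-point reduction to the 10% with gestational diabetes (0.10 × 25 = 2.5 points). The third uses 256/580. With no true difference, the rejection rate stays near 0.049.

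**The case against.** The strongest reply is that this is a small editing slip in a wide composite. To lose event status a woman must be hypertensive, have a ratio in a band 0.11 wide, and have none of the other five components. The limits are the same in both arms, so there is no built-in bias. The illustration in step 6 is placed at the boundary, where almost any reclassification matters; step 7 shows that the decision usually does not change. These points stand, and they bound the likely effect. They do not supply a rule for the affected women.

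The intent also looks clear: with and without proteinuria are complements, so items c and d were presumably meant to cover all hypertensive women between them. That is probably right, but the SAP says its listed definitions apply. An analyst who counts these women is using a rule the SAP does not contain.

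The protocol is not perfectly clean either. Because each of its items joins ratio and 24-hour protein with an or, a ratio of 0.25 with a 24-hour value below 300 mg meets both 7c and 7d. That woman is still an event under the protocol, so the overlap affects only her label. It does show that discordant results need a rule.

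The damaged fragment in item c may be a PDF reading fault, so no error is alleged there.

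**Conclusion.** The concern holds and must be fixed. As written, SAP 3.1.1 assigns no category to a hypertensive woman whose only urine result is a ratio of 0.19 to below 0.30. Protocol 7d counts the same woman as a primary event. This follows from the printed limits and needs no assumption beyond classification by ratio alone.

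The number of women affected cannot be derived from the documents. The range of 5.8 to 34.8 women rests on an assumed 0.5% to 3% who are in the interval with no other component. The event counts and splits in step 6, and the rates in step 7, are likewise assumptions. No directional bias, loss of power or inflation of type I error is claimed. The priority comes from where the gap lies, in the event definition of the primary endpoint.

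**What to change.** Before unblinding, and before the interim analysis if it has not been run, reconcile protocol 7c-d and SAP 3.1.1c-d to one shared proteinuria criterion:

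- Make the two items meet, so that every hypertensive woman with a urine result falls in exactly one category.
- State whether the 24-hour measure is kept. If it is, give it in both items and say how discordant ratio and 24-hour results are classified.
- State how a hypertensive woman with no urine result is classified, since neither item covers her.

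This review does not say which cut-off is right. With one shared ratio cut-point, women classified by ratio count toward the composite wherever it is set; the choice affects only the separate gestational hypertension and preeclampsia analyses.

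The cost is wording in both documents and some derivation work. The composite rate may shift slightly. Some chart abstraction may be needed: protocol section 8f lists admission laboratory results but names no urine protein field.

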### 2. DESCRIPTIVE STATISTICS

Patient characteristics at randomization will be summarized by randomization group. The two study groups will be labeled as Early (for early gestational diabetes screening 14-18 weeks) and Routine (for routine gestational diabetes screening 20-24 weeks). For continuous variables, means/medians and standard deviations/interquartile ranges will be reported. To assess and/or identify covariates for which adjusted sensitivity analyses might be conducted, Student t-tests will be used to compare means between study groups. Where appropriate, medians and quartiles will be reported and the Wilcoxon rank sum test will be used as an alternative comparison procedure. Categorical measures will be presented as counts and percentages and will be compared using the  $\chi^2$  tests of association to identify potential group differences. For rare outcomes such that the  $\chi^2$  test of association is not appropriate, Fisher's exact test will be used. Balance overall is expected because of the large sample size and we expect approximately 5% to be different by chance, since we are not adjusting these baseline comparisons for multiple testing. Any group characteristics that are identified as statistically significantly different between the two groups at a 0.05 level of significance will be considered as covariates in multivariable models in subsequent analyses of the primary study outcome.

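### SAP 2 and 3.1.2: the primary chi-square ignores the randomization strata, covariates are chosen by baseline p-values, and a triggered odds-ratio model competes with the primary risk ratio

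*SAP*

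**What the plan says.** **Primary test.** SAP 3.1.2 states that a chi-square "test of association will be used to evaluate whether the rate of the primary outcome differs between the treatment groups". The analysis is intention-to-treat, and "Risk ratios (RR) and 95% confidence intervals (CIs) will be computed and presented". SAP 3.2 writes the reject rule on the chi-square scale: above 7.82 at the interim and above 3.91 at the final look (level 0.048).

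**Strata.** SAP 1 stratifies randomization by BMI (≥40 vs <40) and by site. Protocol item 2 (Randomization) gives BMI >40.0, does not mention site, and describes a simple scheme with envelopes drawn by BMI group. In the analysis, the strata serve a Breslow-Day homogeneity test. Site, but not the BMI stratum, is also a named term in the contingent model, whose covariate set "consists of all covariates in the model including site".

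**Covariate choice.** SAP 2 says that characteristics "statistically significantly different between the two groups at a 0.05 level of significance will be considered as covariates in multivariable models" for the primary outcome. SAP 3.1.2 thinks it unlikely that important "covariates (such as race, BMI or age) will be imbalanced through the" randomization process.

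**Status of the adjusted model.** SAP 2 gives the purpose of the baseline tests as: "To assess and/or identify covariates for which adjusted sensitivity analyses might be conducted". SAP 3.1.2 is firmer: "In the unlikely event that imbalance occurs, adjustment for covariates will be made by modeling the log-odds of the outcome using multivariable logistic regression". It continues "To address the hypothesis of interest for primary hypothesis #1, we will perform a statistical test of" no treatment coefficient in that model, and quantifies the effect as an odds ratio.

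**The concern.** There are three linked weaknesses.

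1. The design stratifies on BMI and site, but the deciding test does not use them. A Breslow-Day test asks whether the effect varies across strata; it adjusts nothing. If BMI or site predicts the composite, some precision is lost.
2. In a randomized trial, a baseline difference with p<0.05 is a chance event, as SAP 2 itself concedes. The rule selects any given characteristic in about 5% of trials, however strongly it predicts outcome. Race, BMI and age, which SAP 3.1.2 gives as examples of important covariates, would usually go unused.
3. If the rule fires, the SAP does not say which result decides primary hypothesis #1. Several sentences of SAP 3.1.2 point to the logistic model: adjustment is mandatory, its coefficient is tested for the primary hypothesis, and the effect is quantified from it. SAP 2 and the 3.2 stopping values point to the chi-square. The effect measure changes too, from risk ratio to odds ratio.

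**Working it through.** **Inputs from the SAP.** 580 per arm, 1,160 in total (3.1.3); 10% GDM incidence and 50% vs 25% event rates among women with GDM (3.1.3); cut-offs 7.82 and 3.91 (3.2); covariate rule p<0.05 (2).

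**Assumed, because the documents give no value.** Composite rate in all randomized women, share at BMI ≥40, share at the second site, stratum effects, covariate strength, number of baseline tests.

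**1. The plan's own figures reproduce.** Two proportions 0.50 vs 0.25, two-sided 0.05, 80% power, pooled variance: 58 per group; 58/0.10 = 580 per arm. For 1 df, P(χ²>3.91) = 0.0480 and P(χ²>7.82) = 0.0052. The pair is the classical two-look O'Brien-Fleming boundary at half information, overall level 0.0500. A Cochran-Mantel-Haenszel (CMH) test also has 1 df, so both cut-offs carry over.

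**2. How often the adjustment fires.** With k independent baseline tests the chance of at least one p<0.05 is 1 − 0.95^k:
- k = 3: 0.143
- k = 10: 0.401
- k = 20: 0.642

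The SAP gives no k. If allocation is balanced within BMI strata, BMI fires less often and the first figure moves towards 1 − 0.95² = 0.098.

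**3. Stratified test against chi-square, N = 1,160, cut-off 3.91.**

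*BMI strata only* (control rate 48%, 20 to 50% at BMI ≥40, risk ratio 0.82, a difference of 0.48 × 0.18 = 8.6 points):

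| Risk gap between BMI strata | CMH minus chi-square (power points) |
|---|---|
| 5 points | 0.0 |
| 10 points | 0.0 to 0.3 |
| 20 points | 0.5 to 1.2 |

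*BMI × site, four strata*: about 0 to 1.3 points at risk ratio 0.82. In a version with 40% at BMI ≥40, 15% at the second site, simple randomization and an effect sized for roughly 80% power, the gain is about 0.5 point at stratum odds ratios 1.5/1.5, about 1.3 at 2/1.5, and 3 to 3.5 only at 3/2.

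*Chi-square size under the null*: 0.048 to 0.049 with simple randomization, and 0.044 to 0.049 with allocation balanced within BMI strata. At stratum odds ratios 3/2 with balanced allocation it falls to 0.040. Departures are on the conservative side.

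**4. If only women with GDM benefit.** The SAP inputs imply 0.10 × (50 − 25) = 2.5 points overall. At control 50%, SE = √[(0.50×0.50 + 0.475×0.525)/580] = 0.0293, z = 0.025/0.0293 = 0.85, and power at cut-off √3.91 = 1.977 is 0.133. It is 0.152 at control 30%. The gain from stratifying is then 0.0 to 0.3 point (BMI only) and at most about 0.9 (four strata).

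**5. Fixed covariate set against the p<0.05 rule** (580 per arm, three prognostic covariates among 3 or 10 tested, control rate about 45%, 10,000 runs per cell):

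| Treatment log-odds | Covariate log-odds per SD | Chi-square | p<0.05 rule | Fixed set |
|---|---|---|---|---|
| −0.35 | 0.2 | 0.805, 0.804 | 0.806, 0.803 | 0.817, 0.819 |
| −0.35 | 0.4 | 0.744, 0.744 | 0.746, 0.749 | 0.786, 0.789 |
| −0.105 (about 2.5 points) | 0.2 | 0.137, 0.136 | 0.137, 0.136 | 0.140, 0.142 |
| −0.105 (about 2.5 points) | 0.4 | 0.123, 0.123 | 0.120, 0.122 | 0.131, 0.133 |

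The rule selects each prognostic covariate in 4.8 to 5.2% of runs and recovers at most 0.5 point. A fixed set gains about 1 to 4 points at the larger effect and 0.3 to 1.0 at the smaller.

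**6. Two candidate results.** Under the null, rejecting if either the chi-square or the triggered model rejects has size 0.049 to 0.052 (Monte Carlo SE 0.002) against 0.048. The tests disagree in 0.4 to 2.2% of runs. On scale, 50% vs 41.8% is a risk ratio of 0.418/0.50 = 0.84 but an odds ratio of 0.418/0.582 = 0.72.

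**The case against.** An unadjusted intention-to-treat chi-square with a risk ratio is a legitimate, pre-specified analysis. The Protocol describes simple randomization with no block size; without restricted allocation the strata are ordinary baseline covariates and ignoring them leaves the size at about 0.048. With balanced allocation, stratifying does not change the variance of the estimate; it only removes some conservatism. All of this stands, and it limits the point to precision and clarity.

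A reader might infer more in three ways.

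- *That the primary test is invalid, or that two candidate tests inflate type I error.* Neither is supported: the simulated size does not materially exceed nominal, and taking either result moves it only to 0.049 to 0.052.
- *That the trial's decision forgoes the 1 to 4 points shown for a fixed covariate set.* It does not, because the adjusted analysis belongs under sensitivity, as SAP 2 has it. Only the stratified-test gain reaches the reject decision.
- *That the SAP replaces the chi-square by the logistic test.* The 3.2 cut-offs and SAP 2 say otherwise. What the documents show is an unresolved conflict.

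It can also be said that changing the primary test is not free once a comparison by group has been seen. That is right. SAP 3.2 plans one after 600 women, and the documents do not show whether it has taken place. The fix is conditioned on this.

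**Conclusion.** The point holds as a low-severity, nearly free improvement. The deciding chi-square is valid but does not use the strata. At moderate assumed stratum effects this costs about 0 to 1.3 power points at a risk ratio of 0.82 and less than 1 point at an overall difference of 2.5 points. It costs more only if BMI and site are very strongly prognostic, and nothing if they are not prognostic. Choosing covariates by baseline p-value has no statistical rationale here and recovers almost none of what a fixed set would.

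The conflict over which result decides rests on the text alone and needs no assumption. It spans several sentences of SAP 3.1.2 and would surface whenever a baseline test happens to reach p<0.05. The power figures, by contrast, rest on event rates, stratum shares and covariate strengths that the documents do not supply.

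**What to change.** 1. **Strata and primary test.** Confirm the strata actually used, since the Protocol (BMI >40.0, no site) and the SAP (BMI ≥40, site) differ. Then make the primary test a CMH test stratified by BMI stratum as randomized and by site, with the Mantel-Haenszel risk ratio. Keep 7.82 and 3.91. At the interim, which excludes Ochsner, stratify by BMI only. Make the change before the interim comparison by group, or have it made by people blinded to that comparison. Otherwise keep the chi-square as primary and report the CMH result as a pre-specified supporting analysis.
2. **Adjusted analysis.** Drop baseline p-values as the covariate selector. Pre-specify one adjusted sensitivity analysis with BMI stratum, site, age and race, reported as a risk ratio (modified Poisson with robust standard errors, or standardized logistic). Any gain in precision applies to that analysis only.
3. **Hierarchy.** Reword every sentence in SAP 3.1.2 on the triggered model, namely that adjustment is mandatory, that its coefficient is tested for primary hypothesis #1, and that the effect is an odds ratio, so that one stated test and the risk ratio decide.

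Items 2 and 3 stand even if the chi-square stays primary. The cost is a dated SAP amendment before the final unblinded analysis and a check of the BMI boundary and site lists behind the envelopes. The SAP already treats race, BMI and age as baseline covariates, so no new data are needed.
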